1	1		1 st						
1	2			2 nd					
2	1				3 rd				
2	2	4 th							
	pre-implementation implementation post-implemen- tation administrative data collection only								
	Figure 4: Stepped wedge design for the 8 participating STRIDE VAMCs (4 per stratified block, 2 per wave), with a 3- month period to implement training for each site								

Randomization procedure. For each stratified block, we will have two randomizations due to the stepped-wedge design and comparison of two implementation strategies. First, in each stratified block, the 4 VAMCs will be randomized to either wave 1 or wave 2, then within wave each VAMC will be randomized to either REP alone or REP + CONNECT. Within each block and wave combination, one VAMC will use REP alone and the other will use REP + CONNECT for

STRIDE implementation. In each stratified block, the four VAMCs will be in the pre-implementation period during the first 3-month recruitment window. There will be a 3-month interval implementation period in each block where the intervention is rolled out.

STRIDE Participating sites. We will recruit sites in blocks of 4 based on our stratified design described above for a total of eight sites for participation. With assistance from our operational partners ([name] from GEC and [name] from PM&R), we will recruit the sites on a volunteer basis to complete the cohort of eight. To ensure that sites are similar enough to compare between arms, sites are required to have a minimum average daily census of 20 general medicine patients per day. We will conduct site visits at all participating sites prior to implementation to obtain additional important contextual information and baseline data for analyses.

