We hypothesize that sites randomized to REP + CONNECT will have higher penetration (for STRIDE that is the proportion of eligible patients with \geq 1 documented walk during hospitalization, higher total daily minutes of activity and distance walked, and higher proportion of eligible patients who report their providers wanted them to walk while they were in the hospital; and for iHI-FIVES that is the proportion of eligible caregivers reached by iHI-FIVES in a 6-month interval and the proportion of providers involved in caregiver support who refer caregivers to participate in iHI-FIVES in a 6-month interval) and **fidelity** (higher proportion of STRIDE participants with \geq one documented supervised walk, and with \geq 10 minutes of daily walking); for iHI-FIVES proportion of sites that delivered at least two rounds of iHI-FIVES trainings in a 6-month interval during post-implementation and the proportion of training rounds from the total number offered in which the full iHI-FIVES core curriculum topics were covered). For Aim 1, outcomes are defined in the post-implementation period only and the primary analyses will be for the outcomes in the first post-implementation 3-month period so that analysis will not be confounded with time since implementation. For the dichotomous outcomes, we will use logistic regression models⁵⁵⁻⁵⁷ where the main predictor of interest will be REP vs. REP + CONNECT adjusting for clustering of VAMC with either a random effect or by conditioning. For continuous outcomes, we will use linear mixed regression models.⁵⁸ Adjustments for patient characteristics and a random effect for hospital ward may also be added. In hospitals that have multiple post-implementation 3-month measurement times, we will examine how fidelity and penetration outcomes change over time using descriptive methods (e.g. plots, descriptive statistics, subgroups).

In addition to testing the above quantitative hypotheses, we will use semi-structured interviews with providers to elicit their experience with implementation process and evaluation of outcomes. Specifically, we will ask providers questions about team processes, for example, *How do team members communicate with each other*

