As described for Aim 1, Aim 3 outcomes are defined in the first post-implementation 3-month period so that analyses will not be confounded with time since implementation. To examine the relationship between team function and dichotomous implementation outcomes, we will use logistic regression models⁵⁷ where the main predictors of interest will be the baseline TDM[©] scores (e.g., overall, and team dimensions such as cohesion and role clarity) adjusting for clustering of VAMC with either a random effect or by conditioning.^{55,56} Other responses from the provider survey instrument may collectively reflect other dimensions of team function. Using exploratory factor and cluster analysis methods, the implementation core will determine the appropriateness (i.e., with our operational partners) and reliability of constructing other composite measures of team function that will be incorporated in quantitative analysis to examine teams' mediating/moderating effects on implementation outcomes. For continuous outcomes, we will use linear mixed regression models.⁵⁸ In VAMCs that have multiple postimplementation 3-month measurement times, we will examine how fidelity and penetration outcomes change over time by TDM[©] scoreteam function using descriptive methods (e.g. plots, descriptive statistics, subgroups). Adjustments for covariates and a random effect for VAMC ward may also be added. If scores of team function are associated with implementation outcomes, we will explore whether they differentially affect implementation outcomes by patient and facility characteristics. If we find in Aim 1 that the implementation strategy REP + CON-NECT improves implementation outcomes compared to REP alone, we will examine whether team function mediates or moderates this effect following methods of MacKinnon⁵² and Kraemer.^{61,62} These quantitative findings from Aim 3 will be complemented by additional analyses of context sensitivity as described earlier.

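### Aim 1 compares REP with REP + CONNECT on 4 v 4 VAMCs and names no small-sample method: conditioning on VAMC cannot estimate the effect, and a random effect with large-sample inference has a false-positive rate of about 7-14%

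*Combined protocol and SAP*

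**What the plan says.** Under *Randomization procedure* (STRIDE), sites are paired by block and wave, and within each pair "one VAMC will use REP alone and the other will use REP + CONNECT". *STRIDE Participating sites* sets recruitment in blocks of four, "for a total of eight sites for participation". Strategy is therefore assigned to whole VAMCs, four per arm. iHI-FIVES uses the same scheme.

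Under *Analyses*, Aim 1, "the primary analyses will be for the outcomes in the first post-implementation 3-month period", so each site supplies one period of data. Dichotomous outcomes get logistic regression "where the main predictor of interest will be REP vs. REP + CONNECT adjusting for clustering of VAMC with either a random effect", with conditioning as the alternative. "For continuous outcomes, we will use linear mixed regression models". Aim 3 offers the same two adjustments ("adjusting for clustering of VAMC with either a random effect or by conditioning") in models "where the main predictors of interest will be the baseline TDM" scores.

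The documents name no variance estimator, reference distribution, degrees-of-freedom method, permutation test or site-level analysis for these comparisons. Aim 1 has no stated alpha, power or sample size. The 0.05 under *Sample size estimate* belongs to the patient-outcome calculations.

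**The concern.** The randomised unit is the VAMC, and there are eight. However many patients each site contributes, the strategy contrast has at most 6 degrees of freedom, or 3 if the four block-wave pairs are respected. Two problems follow.

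- **Conditioning.** Every patient in a VAMC has the same strategy. Once the model conditions on VAMC, nothing is left from which to estimate the strategy effect.
- **Random effect.** A Wald z or chi-square test treats the between-site variance as known. With eight sites it is poorly estimated, and maximum likelihood also biases it downward. Intervals are then too narrow and true nulls are rejected too often.

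This is the lead question for both programmes. The *Impact* section says that REP alone, as the cheaper strategy, may be preferred if it does equally well. A false positive would therefore favour the costlier strategy.

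**Working it through.** **1. The plan's own figure.** Aim 1 has none. The only STRIDE power statement concerns discharge to skilled nursing: 20% base rate, 10% drop, 8 sites, 5 periods, 50 per site-period, ICC 0.02-0.6, power at least 80%. The Hussey and Hughes variance is

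Var = Iσ²(σ² + Tτ²) / [(IU − W)σ² + (U² + ITU − TW − IV)τ²].

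With two sites per step, I = 8, T = 5, U = 20, W = 120 and V = 60, so the bracketed coefficients are 40 and 120. Take σ² = 0.16/50 = 0.0032 and τ² = 0.16 × ICC/(1 − ICC).

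- ICC 0.02: SE = 0.0310, power = Φ(0.1/0.0310 − 1.96) = 0.897.
- ICC 0.6: SE = 0.0326, power = 0.865.

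The statement reproduces if the drop is absolute, from 20% to 10%. It says nothing about REP v REP + CONNECT.

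**2. Inputs for Aim 1.**
- 4 v 4 sites, one period each (*Randomization procedure*; *Analyses*, Aim 1).
- ICC 0.02-0.6, 50 per site-period and two-sided 0.05, all borrowed from *Sample size estimate*. Sidedness is my assumption.
- About 30 per site-period for survey measures (*Patient surveys*). I read this as per site, which fits 4 × 150 + 4 × 90 = 960 = 32 × 30.
- About 400 per site-period from the anticipated maximum: 16,000/(8 × 5). The nearly 15,000 reported under *QUERI ADIL* gives about 375.

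**3. Exact tail areas.** The difference in arm averages of site means, divided by its standard error from the pooled between-site variance, follows t with 6 df under the null. REML divides the between-site sum of squares by 6, and ML divides it by 8.
- REML with z: P(|t6| > 1.96) = 9.8%.
- ML with z: P(|t6| > 1.96 × √(6/8)) = P(|t6| > 1.697) = 14.1%.

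**4. Linear mixed model, 1,000,000 replicates**, with the site variance truncated at zero:

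| Patients per site | ICC | REML, z | ML, z | REML, t6 |
|---|---|---|---|---|
| 30 | 0.02 | 6.8% | 8.9% | 2.7% |
| 50 | 0.02 | 7.9% | 10.5% | 3.3% |
| 50 | 0.1 | 9.7% | 13.9% | 4.9% |
| 400 | 0.02 | 9.7% | 14.0% | 5.0% |
| 400 | 0.6 | 9.8% | 14.0% | 5.0% |

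With no site variance at all, z gives about 4-5%.

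**5. Random-intercept logistic model, ML, 2,000 replicates per setting.** The assumed event proportions are 10%, 20% or 50%, and the ICC is on the latent scale, up to 0.3. Simulation error is about ±1.5 points.

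| Patients per site | ICC | Wald z | Likelihood ratio | Wald with t6 | Site-level t |
|---|---|---|---|---|---|
| 50 | 0.02 | 7.9-10.3% | 6.7-8.0% | 3.1-4.8% | 5.2-5.7% |
| 50 | 0.1-0.3 | 12.0-13.0% | 9.3-10.6% | 6.7-7.4% | 4.2-5.4% |
| 250-400 | 0.02-0.3 | 12.8-13.6% | 9.2-9.8% | 6.4-7.3% | 2.8-5.1% |

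**6. Randomisation limit.** Within the four pairs there are 2⁴ = 16 strategy allocations, so the smallest two-sided randomisation p is 2/16 = 0.125. If waves are re-drawn too, each block has 6 strategy splits, and 2/36 = 0.056 is still above 0.05.

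**7. Price of the correction.** The 6-df critical value is 2.447, and 2.447/1.960 = 1.25. The 3-df value is 3.182, and 3.182/1.960 = 1.62.

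**The case against.** The strongest reply is that the plan never says z or chi-square will be used. It is silent, and a t reference on 6 df keeps the linear mixed model at or below 5%. That stands. A reader might infer that the planned test simply has a 10-14% error rate, but the documents do not support this. The inflation is conditional on large-sample inference, and at 30-50 patients per site with ICC 0.02 it starts near 7%. Silence is not a safeguard, however, because it leaves the reference distribution to be chosen after the data are seen.

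Three further inferences go beyond the documents.
- **iHI-FIVES.** The simulated rates should not be carried over. Its Aim 1 outcomes concern caregivers reached, referring providers, training rounds and sites, and none of these was simulated.
- **Aim 3.** The mediation and moderation work follows if Aim 1 finds that REP + CONNECT improves implementation. The text does not make a significant p-value the trigger.
- **Team scores.** The Team Development Measure may be analysed at individual or team level, so it is not necessarily constant within a site. No Aim 3 error rate was computed.

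It is also fair that Aim 1 is read alongside qualitative data, so the p-value is not the only evidence. That does not make an interval that is too narrow acceptable.

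**Conclusion.** The point holds in conditional form. Of the two adjustments offered for Aim 1, conditioning cannot estimate the strategy effect. The random effect is valid only with a small-sample correction that the plan does not name. Under z or chi-square inference the false-positive rate is about 7-14% against a nominal 5%, depending on patients per site, ICC, estimator and test.

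This rests on normally distributed site effects, equal site sizes, and an alpha and ICC range borrowed from the patient-outcome sample size. The logistic results also rest on assumed event proportions. The missing method, and the failure of conditioning for a strategy fixed within a site, depend on none of these.

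**What to change.** In *Analyses*, Aim 1:
- Delete the conditioning option.
- Make the primary test and interval a site-level comparison, with one proportion or mean per VAMC and a t reference. Alternatively, use a REML linear mixed model with Kenward-Roger or between-within degrees of freedom. Putting t6 on the ML logistic Wald test is a weaker remedy, since it still gave up to 7.4%.
- State before the data are seen whether the four block-wave pairs are ignored (6 df, 2.447) or respected (3 df, 3.182).
- State the alpha and sidedness for Aim 1.
- Say that the 16 within-pair allocations allow no randomisation p below 0.125, so any p < 0.05 is model-based.

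Use the same basis in Aim 3 for any predictor that is constant within a site.

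The change is to wording only, but it has a price. With the same standard error, intervals are about 25% (6 df) to 62% (3 df) wider than under z. Measured against an ML standard error, the 6-df widening is about 44% (1.248 × √(8/6) = 1.44). Power for REP v REP + CONNECT is lower, and the plan should acknowledge this.

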tion) observations and every cluster (VAMC) switches from control to be exposed based on their randomly assigned post-implementation start date (step) during recruitment months of the study. Transition to intervention condition will occur at 6-month intervals. The pre-observation period occurs from time 0 (stratified block 1) to the beginning of post-implementation at an individual VAMC. Each site will provide at least two rounds of iHI-FIVES training in each 6-month period (the basic iHI-FIVES training, e.g., core component, means that "one round" is defined as "4 weekly classes") covering core sessions listed in Table 5. Ideally, each class in a round would be offered on consecutive weeks, but the sites will have discretion on scheduling around holidays. The National Director of Caregiver Support felt that offering 2 rounds of iHI-FIVES in a 6-month period (total of 8 hours instructional time, and additional recruiting and recording keeping time) is reasonable for CSC workload.

2.5.3.c. Randomization procedure. Similar to implementation Project 1, there will be two randomizations due to the stepped-wedge design and comparison of two implementation strategies. First, in each stratified block, the 4 VAMCs will be randomized to either wave 1 or wave 2, then within wave randomized to REP alone or REP + CONNECT for iHI-FIVES implementation. In each stratified block, the 4 VAMCs will be in the pre-implementation period during the first 6-month recruitment window. Within each block, sites will begin offering iHI-FIVES training to CGs during the first post-implementation period and will continue for the remaining post-implementation 6-month intervals.

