Team characteristics and processes. Features of team characteristics and processes will be assessed using the Team Development Measure (TDM[©]), a 31-item questionnaire, which characterizes the degree to which groups have the characteristics of highly effective teamwork in place.^{49,50} The TDM[©] is ideally suited for Function QUERI's evaluation of teams for several reasons. First, the instrument has been tested in a variety of healthcare settings (e.g., administrative, inpatient and outpatient) and maintains psychometric strength when applied to 2040 Function QUERI PI [name] AMD 23 5.17.2023 Page 11 of 42

group size ranging from 3 to 43 members. Second, the TDM[©]'s validated instrument design measures team functioning from the perspective of individual members of teams, allowing for data collection and analysis at the individual and team-level.

Although TDM[©] responses generate a summative score describing overall team development, items from the TDM[©] also cluster to reflect the four key dimensions of team function: communication, role clarity, cohesion, and goal and means clarity.⁴⁹ This will enable the implementation core to 1) assess baseline and post-implementation changes in dimensions of team function, 2) identify variations in team strengths and weaknesses within and across clinical programs at participating sites, and 3) assess the dimensionality (e.g., one summative measure of team function or multiple measures of team function) and predictive power of team function on implementation and program outcomes to inform future implementation efforts.

The implementation core will examine other important features of teams, including size, composition and the degree to which team membership spans boundaries (e.g., clinical, professional, etc.) by supplementing the TDM with additional survey items. For example, we will also describe team communication channels (internal, external), decision-making, and establishment of routines (Table 2). The team survey will take roughly 15-20 minutes to complete.

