Quantitative analyses for Aim 2 will be conducted at the level of the patient, utilizing all available data to evaluate STRIDE effectiveness on defined dichotomous, count and continuous outcomes. The overall anticipated sample size of eligible STRIDE patients during pre- and post-implementation periods is 2000. The anticipated maximum sample is 16,000. Only a subset of STRIDE eligible patients will receive survey measures in both the pre- and post-implementation periods. We will use random effect linear (continuous outcomes), negative binomial (count outcomes), or logistic (dichotomous outcomes) models appropriate for the stepped-wedge design which account for the correlation of patients within the same VAMC.^{34,60} For example with a continuous outcome, I VAMCs, T time points, N individuals per VAMC per time interval, the model is: $Y_{ijk} = \mu + \alpha_i + \beta_j + X_{ij}\theta + e_{ijk}$, where α_i is the random effect for the ith VAMC, β_j is a fixed effect that captures time trends, and X_{ij} is an indicator of the intervention mode for the ith hospital at time j (=0 prior to intervention and =1 post intervention), and θ is the measure of the effect of the intervention. Adjustments for patient characteristics and a random effect for hospital ward may also be added.

Qualitative data will be collected via 30-45 minute semi-structured telephone interviews with a sample of patients in STRIDE. Interviews will be audio recorded. We will ask patients about whether they found STRIDE to be helpful for them and in what ways and if they have suggestions for improvement. We will analyze data using conventional content analysis, in which we will transcribe interviews and then code text with descriptive labels that are developed as we read through transcripts. Data will be coded by a team process as described in Aim 1. Findings from Aims 1 and 2 will be supplemented by **budget impact analyses**

Aim 2b: To examine the **impact** of iHI-FIVES on key patient and caregiver outcomes.

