Sample size estimate. For STRIDE, sample size calculations were conducted for patient-level analyses evaluating impact of STRIDE on discharge to skilled nursing facility. The sample size calculation was done based on a complete stepped-wedge design using Hussey and Hughes (2007) method.⁶⁰ The sample size is based on the following assumptions for the discharge to skilled nursing facility outcome: 1) base discharge rate to skilled nursing of approximately 20%; 2) 10% drop in discharge rate after STRIDE, determined as a clinically significant gain in the outcome; 3) intracluster correlations (ICC) ranging from 0.02 to 0.6 for patients within the same hospital; 3) 8 hospital sites with 5 3-month assessment periods; and 4) alpha=0.05, power>80%. A total sample of 2000 patients (~250 per hospital, 50 per 3-month interval) will result in ≥80% power to detect a 10% reduction in discharges to skilled nursing facilities. The anticipated maximum sample is 16,000. For iHI-FIVES, the sample size calculation was done based on a complete stepped-wedge design using Hussey and Hughes (2007) method.⁶⁰ The overall anticipated number of Veteran patients will be 15,000-18,000 with a minimum sample size of 400 subjects (at least 50 per VAMC, 20 per 6-month interval). The power calculation for this sample size is based on the following assumptions for days not at home: 1) 8 is the baseline mean number of days not at home over 6 months; 2) 2-day reduction in days not at home over 6 months; 3) coefficient of variation (CV) ranging from 0.3 to 0.5 for assessments on participants within the same VAMC; 4) 8 VAMCs with five 6-month assessment intervals; and 5) alpha=0.05, power>80%. A minimum sample of 400 Veterans will result in at least 80% power to detect a mean reduction of 2 days not home assuming variance equal to the mean (Poisson distribution).

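### Aim 1 allows conditioning on VAMC, which removes the REP versus REP + CONNECT contrast; the random-effect option in the same sentence still estimates it

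*Combined protocol and SAP*

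**What the plan says.** In the STRIDE randomization procedure, within each block and wave, "one VAMC will use REP alone and the other will use REP + CONNECT". The iHI-FIVES randomization procedure (2.5.3.c) allocates sites to waves, "then within wave randomized to REP alone or REP + CONNECT for iHI-FIVES implementation". In both projects the strategy belongs to the whole VAMC.

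Under Analyses, Aim 1, "outcomes are defined in the post-implementation period only", and the first post-implementation period is primary. REP versus REP + CONNECT is the main predictor. Dichotomous outcomes use logistic regression, "adjusting for clustering of VAMC with either a random effect or by conditioning", with no rule for choosing between the two. Continuous outcomes use linear mixed models. No reference distribution is named.

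Aim 3 repeats the same clustering phrase for baseline TDM scores. The section on team characteristics describes the TDM as "allowing for data collection and analysis at the individual and team-level".

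For STRIDE Aim 2a the models are to "account for the correlation of patients within the same VAMC". The example equation has one random intercept per VAMC, period effects common to all VAMCs, and the intervention indicator. In addition, "a random effect for hospital ward may also be added".

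**The concern.** Conditioning on a cluster uses only comparisons made within that cluster. When every patient in a VAMC has the same strategy, there is no such comparison. One of the two models allowed for dichotomous Aim 1 outcomes therefore cannot address the question that defines Aim 1 in both projects. The optional ward effect does not help, because wards lie inside VAMCs. Striking the option leaves a usable model but no named reference distribution, and with four sites per strategy that choice matters.

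The Aim 2a example raises a separate question. If discharge or length of stay drifts differently from VAMC to VAMC, a single intercept per VAMC understates the standard error, and more so as the sample grows. A ward effect that is constant over periods does not absorb this drift.

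**Working it through.** **Aim 1: is the contrast estimable?** The documents give no power figure for this comparison, so there is none to reproduce.

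1. Inputs: 8 VAMCs, 4 per strategy, strategy constant within VAMC, post-implementation data only.
2. Design matrix: 8 VAMC indicators plus arm make 9 columns. Arm equals the sum of the four REP + CONNECT indicators, so the rank is 8.
3. Conditional likelihood: VAMC i has n patients, m events and constant arm value a. Its contribution is exp(b·a·m) / [C(n,m)·exp(b·a·m)] = 1/C(n,m), in which b does not appear. In simulated data (8 sites of 50, true log odds ratio 1.0) the conditional log-likelihood was −241.9135 at b = −5, −1, 0, 1 and 5.
4. What remains estimable: four block-wave indicators plus arm have rank 5 of 5, and VAMC indicators plus a score that varies by ward have rank 9 of 9. Conditioning on VAMC therefore removes a TDM score only if it is aggregated to the VAMC.

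**Aim 1: does the reference distribution matter?** Comparing 4 with 4 site means leaves 8 − 2 = 6 df; modelling the four pairs leaves 4 − 1 = 3 df.

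- Normal cut-off: P(|t6| > 1.96) = 9.8%; P(|t3| > 1.96) = 14.5%.
- Interval width: 2.447/1.960 = 1.25; 3.182/1.960 = 1.62.
- Simulation under assumed values (base rate 30%, ICC 0.02–0.05, 50–375 patients per site): random-intercept logistic ML rejects in 7.5–13.6% with a normal reference and 2.9–7.5% with t on 6 df. Site proportions with t on 6 df reject in 4.2–5.4%.

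**Aim 2a: the plan's own power figure.** Inputs from Sample size estimate: "8 hospital sites with 5 3-month assessment periods", 50 patients per hospital and period, 20% base rate, 10-point drop, ICC 0.02–0.6. With four steps of two hospitals, U = 20, W = 120 and V = 60. The Hussey and Hughes variance is then

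8σ²(σ² + 5τ²) / (40σ² + 120τ²).

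At ICC 0.02 with variance 0.16: τ² = 0.0032 and σ² = 0.98 × 0.16/50 = 0.003136. The variance is 0.000942 and the SE 0.0307, so power is Φ(0.10/0.0307 − 1.96) = 90%. Over the stated ICC range and the usual choices of binomial variance, power is 86.5–99.98%. The stated figure of at least 80% is reproduced.

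**Aim 2a: the missing term.** I split total variance into ICC × r (VAMC), ICC × (1 − r) (VAMC-by-period) and 1 − ICC (residual). The single-intercept linear model was fitted to the expected sums of squares. With k = true SE / model SE, type I error is 2Φ(−1.96/k). The ratio r is not in the documents; 0.95 to 0.80 is assumed, with ICC 0.02 and 0.05. The second sample size is the trial cohort of nearly 15,000 described in the ADIL data source, or 375 per cell.

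| Patients | ICC | r = 1 | r = 0.95 | r = 0.90 | r = 0.80 |
|---|---|---|---|---|---|
| 2,000 | 0.02 | k 1.00, 5.0% | 1.02, 5.5% | 1.04, 6.1% | 1.09, 7.1% |
| 2,000 | 0.05 | 1.00, 5.0% | 1.06, 6.4% | 1.12, 7.9% | 1.22, 10.8% |
| 15,000 | 0.02 | 1.00, 5.0% | 1.17, 9.5% | 1.32, 13.8% | 1.58, 21.5% |
| 15,000 | 0.05 | 1.00, 5.0% | 1.41, 16.3% | 1.72, 25.4% | 2.21, 37.5% |

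**The case against.** The case for leaving the text alone has real force. The usable model stands in the same sentence. The rank deficiency can be seen from the randomization scheme before any data exist. Conditioning returns no estimate, so it cannot return a misleading one. All of this stands, and it limits the harm.

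Three stronger readings are tempting, and the documents do not support them.

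- A reader might infer that Aim 1 cannot be answered, or that its replacement model would have to be invented after the data are seen. The random effect is already written down; only the reference distribution is open.
- A reader might infer that Aim 1 runs at 10% type I error. That follows only from a normal reference, which the plan never states. It is a reason to name the reference, not an error in the text.
- A reader might infer that the Aim 2 intervals are too narrow. The equation is offered as an example for a continuous outcome, the governing text asks for models suited to a stepped wedge, and the ratio r is not given. The calculation also uses the complete 8 × 5 layout of the power section, not the staggered blocks with a rollout window. The ADIL analysis of the same trial data does say that it will allow for effects within and between periods, without defining them. That makes the term worth adding but does not show that Aim 2 is wrong.

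It is also fair to object that one remedy does not suit every outcome. The iHI-FIVES fidelity measure based on sites delivering two rounds is one yes or no per site in a single interval. A VAMC random intercept cannot be identified from that.

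**Conclusion.** The conditioning option is wrong as written for REP versus REP + CONNECT in STRIDE and iHI-FIVES. This is a matter of algebra and rests on no assumed value. It affects dichotomous Aim 1 outcomes only, and in Aim 3 only predictors measured solely at VAMC level. The random-effect option and the linear mixed models still estimate the contrast, so the practical harm is modest and the correction should simply be made.

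The unnamed reference distribution is an omission that matters with 4 versus 4 sites.

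The Aim 2a point is secondary and conditional. Under the assumed ICC and r, type I error is 5.5–10.8% at 2,000 patients and 9.5–37.5% at 15,000; at r = 1 it is 5%.

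**What to change.** 1. In Analyses, Aim 1, delete the conditioning option for REP versus REP + CONNECT, for both projects. In Aim 3, delete it for predictors measured only at VAMC level; keep it for TDM scores that vary by ward or person.
2. For outcomes with many patients, caregivers or providers per site, name in advance either site-level proportions or the VAMC random intercept as primary, with t on 6 df, or 3 df if the four block-wave pairs are modelled. Site-level proportions hold 5% more closely in the simulation above.
3. Report the iHI-FIVES two-rounds outcome descriptively or with an exact 4 versus 4 comparison. The smallest two-sided Fisher p is 2/C(8,4) = 2/70 = 0.029, reached only when all four sites in one arm succeed and none in the other.
4. Secondary: add a VAMC-by-period random effect to the Aim 2a models for discharge and length of stay.

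**Cost.** Wording only, with no new data. Aim 1 intervals are 25% wider on 6 df, or 62% on 3 df, than with a normal reference. With a 30% base rate, ICC 0.02–0.05 and 50–375 patients per site (all assumed), the difference detectable with 80% power is 16–29 points on 6 df, against a nominal 14–24. Item 4 also widens intervals when the variation is present, and its variance may be estimated at zero.

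Permutation tests are not an easy substitute. For strategy there are 2⁴ = 16 allocations given wave, so the smallest two-sided p is 2/16 = 0.125. For timing there are 6 × 6 = 36. The smallest p is 1/36 = 0.028 only with period effects common to both blocks; with block-specific ones it is 2/36 = 0.056.
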